Appendix D Summary of statistical analyses

Efficacy Analysis

Endpoint	Analysis population	Primary analysis	Supportive analysis	Subgroup analysis	Other analyses
Primary endpoint					
HbA1c: Change from baseline at Week 26, (sotagliflozin 400 mg vs placebo)	ITT	ANCOVA (with missing values imputed by the retrieved dropouts & washout imputation method or by control-based copy reference MI method under MNAR framework): treatment, randomization stratum (HbA1c / SBP at screening), and country as fixed effects, and baseline HbA1c value as a covariate	Tipping point analysis; ANCOVA (with missing values imputed by the retrieved dropouts & washout imputation method or by control-based copy reference MI method under MNAR framework)	Subgroups: race, ethnicity, age, gender, baseline BMI, baseline HbA1c, baseline SBP, duration of diabetes and country.	Summary statistics for observed values and changes from baseline by visit. Graphical presentations for mean changes from baseline (\pm SE) and mean values (\pm SE) by visit. By-visit summary and graph excluding measurements after rescue therapy. See Section 1.6 for additional planned analyses.
Secondary endpoints					
HbA1c (sotagliflozin 200 mg vs placebo), FPG, body weight: Change from Baseline to Week 26; SBP (for patients with baseline SBP \geq 130 mmHg, all patients): Change from Baseline to Week 12 UACR (for patients with baseline UACR $>$ 30 mg/g, all patients): Change from Baseline to Week 26	ITT	ANCOVA (with missing values imputed by the retrieved dropouts & washout imputation method or by control-based copy reference MI Method under MNAR framework): treatment, randomization stratum (HbA1c / SBP at screening), and country as fixed effects, and baseline HbA1c value as a covariate,	No	No	Summary statistics for observed values and changes from baseline by visit. Graphical presentations for mean changes from baseline (\pm SE) and mean values (\pm SE) by visit. See Section 1.6 for additional planned analyses.
Proportion of patients with HbA1c $<$ 6.5%, $<$ 7.0% at	ITT	CMH method stratified on randomization strata (HbA1c / SBP	CMH method stratified on randomization strata (HbA1c	No	By-visit summary and graphs of HbA1c responders

Statistical Analysis Plan

Version: Final 3.0

Lexicon Pharmaceuticals Protocol No. EFC15166

Date of Issue: 21 November 2019

Covance Study ID: 000000155203

Endpoint	Analysis population	Primary analysis	Supportive analysis	Subgroup analysis	Other analyses
Week 26		at screening)	/ SBP at screening): excluding patients with baseline HbA1c values <6.5% (for <6.5% responders) or <7% (for <7% responders) respectively		(<6.5%, <7%). By-visit frequency summary and graphs of HbA1c responders (<6.5%, <7%) excluding patients with baseline HbA1c values <6.5% or <7% respectively. See Section 1.6 for additional planned analyses.
Other endpoints					
SBP (for patients with baseline SBP <130 mmHg), DBP (for all patients and patients with baseline ≥80 mmHg), UACR, UGE, and UGCR, eGFR: change from baseline	ITT	Summary statistics for observed values and changes from baseline by visit.	No	No	Graphical presentations for mean changes from baseline (±SE) and mean values (±SE) by visit as appropriate.
Proportion of patients with >50% decline in eGFR; with progression to end-stage renal disease, with progression/improvement of UACR categories,	ITT	By-visit frequency summary	No	No	By-visit graphical presentation as appropriate
Proportion of patients requiring rescue for hyperglycemia		Summary statistics	No	No	KM plot; List of patients rescued

Statistical Analysis Plan

Version: Final 3.0

Lexicon Pharmaceuticals Protocol No. EFC15166

Date of Issue: 21 November 2019

Covance Study ID: 000000155203

Endpoint	Analysis population	Primary analysis	Supportive analysis	Subgroup analysis	Other analyses
hypoglycemia	Safety	Follow safety guidelines Number (%) of patients with any hypoglycemia, severe hypoglycemia, documented symptomatic hypoglycemia during TEAE period, and incidence rates in 100 patient-years.		Severe hypoglycemia or documented symptomatic hypoglycemia by subgroups: race, age, gender	KM plot time to first event of severe hypoglycemia or documented symptomatic hypoglycemia Documented symptomatic hypoglycemia maybe presented by <54 mg/dL (3.0 mmol/L) as appropriate.
Adverse Events	Safety	Follow safety guidelines	No	Common TEAEs by subgroups: race, age, gender, baseline SBP	
Clinical laboratory data	Safety	Follow safety guidelines	Descriptive	No	No
Vital signs	Safety	Follow safety guidelines	Descriptive	No	No
ECG, Physical examination	Safety	Follow safety guidelines	Frequency summary	No	No

Statistical Analysis Plan

Version: Final 3.0
Lexicon Pharmaceuticals Protocol No. EFC15166

Date of Issue: 21 November 2019
Covance Study ID: 000000155203

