Lexicon Pharmaceuticals Protocol No. EFC15166

Date of Issue: 21 November 2019
Covance Study ID: 000000155203

SAP version number	Date approved	Rationale	Description of statistical changes
2	05-Jun-2019	MedDRA version and dictionary updated	MedDRA version was updated to V22.0 and list of PTs for selected EOSI was updated
2	05-Jun-2019	Update categories of prior antidiabetic medication to cover all patients	Add "no antidiabetic therapy"
3	This version	Change in study Sponsor led to a strategic decision not to report the first step analysis in a standalone CSR	First step analyses will be combined with the second step analysis and both will be conducted at the end of the study in a single CSR The following sections/paragraphs are not applicable Section 2.4.4.4 – the last paragraph Section 3. – the first step analysis details Section 4. – the first data base lock
3	This version		
3	This version	Assess robustness of the ITT-based analyses	Identify possible need to conduct sensitivity analyses for PK anomalies
3	This version	Provide comparative analyses at Week 52 for the primary and secondary efficacy endpoints to further characterize the long-term effects of sotagliflozin	Apply statistical methods specified in Sections 1.6, 2.4.4.1, and 2.4.4.2 to the primary and secondary endpoints at Week 52
3	This version	Based on clinical guidelines for a higher A1C target for patients with chronic kidney disease.	Add another endpoint of proportion of patients with HbA1c <8%, at Week 26 and Week 52

* Change made in Protocol Amendment 1 dated 20-DEC-2017.

The first step analysis was conducted and reported for top line results; it was not used to inform a standalone Clinical Study Report (CSR) limited to just the 6-month data. A single CSR will be written for this study and will include the results coming from the analyses specified at both the first and second steps (see Section 3 of this SAP for more details).

The statistical methods detailed in this section will be performed in addition to those specified in other sections of the SAP. The majority of these additional assessments will serve as sensitivity analyses and will be used to support/qualify the robustness of results from the originally planned analyses.

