The primary and continuous secondary efficacy endpoints for the overall population missing data at Week 26 (or Week 12 for SBP) visit will be imputed using a model built separately in each treatment group and estimated from the patients in the same treatment group who prematurely discontinue the IMP before the Week 26 (or Week 12 for SBP) visit but have the measurement for the endpoint (ie, retrieved dropouts). The imputation model will include the randomization strata and the corresponding baseline value. In cases of non-convergence during the imputations, the offending stratum will be identified and then will be dropped from the model. Considering that the number of retrieved dropout patients in each treatment group is expected to be small, a simple imputation model based on regression will be used with baseline measurement included as the predictor.

An alternative (back-up) imputation method will be used if the number of patients who prematurely discontinue the IMP before the Week 26 (or Week 12 for SBP) visit but have the measurement for the endpoint is < 5 in any treatment groups (ie, an insufficient number of retrieved dropouts to support the imputation method described above). This criterion will be assessed for each primary or continuous secondary efficacy endpoint.

In the back-up imputation method, missing post-baseline endpoint values at Week 26 (or Week 12 for SBP) will be imputed by the washout Multiple Imputation (MI) method under the missing not at random (MNAR) framework.

Missing endpoint data at the Week 26 (or Week 12 for SBP) in all treatment groups (sotagliflozin 400 mg, 200 mg and placebo) are imputed from a model estimated from patients in the placebo group who have the endpoint data available.

For patients in the sotagliflozin 400 mg and 200 mg group with missing data at Week 26 (or Week 12 for SBP), their missing values will be imputed using observed baseline and the observed primary endpoint data from placebo completers; no intermittent values from either placebo or the active treatment groups will be used.

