For placebo patients, missing data will be imputed based on the placebo group data. Intermittent observed values will be used while imputing missing values at Week 26 (or Week 12 for SBP). In cases that a non-monotone missing data pattern occurs at the intermediate visits, these data points will be first imputed in the placebo group using the Markov Chain Monte Carlo (MCMC) option in PROC MI to achieve a monotone missing pattern for all placebo patients. The Week 26 (or Week 12 for SBP) endpoint values will be subsequently imputed from the multiple copies of the original dataset where each copy will have a monotone missing pattern.

The imputation models for the washout MI method will include the randomization strata and the corresponding baseline value. Missing data will be imputed using the regression method. In cases of non-convergence during the imputations, especially for the MCMC application in the placebo non-monotone datasets, graphical measures (eg, trace and autocorrelation plots) will be used to identify the offending variable and once detected, that variable(s) will be dropped from the model and the imputations will be re-run. These re-run models will use the same seed number and number of imputations as used in the original models.

For the overall population each of the completed datasets after the imputation will be analyzed using the Analysis of Covariance (ANCOVA) model with treatment groups (sotagliflozin 400 mg, 200 mg and placebo), randomization stratum of HbA1c ($\leq 8.5\%$, $> 8.5\%$), randomization stratum of SBP (< 130 mmHg, ≥ 130 mmHg), and country as fixed factors, and baseline HbA1c value as a covariate. Results from each analysis will be combined using Rubin's formula, to provide the adjusted mean change in HbA1c from Baseline to Week 26 (or Week 12 for SBP) for each treatment group, as well as the between-group difference (comparing sotagliflozin 400 mg versus placebo and sotagliflozin 200 mg versus placebo) and its associated 95% confidence interval (CI).

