2.4.4.2 Analyses of secondary efficacy endpoints

For continuous secondary efficacy parameters (see [Section 2.1.3](#)) with missing data at baseline, missing data will be imputed using MI under the missing at random (MAR) assumption. Missing data at baseline will be imputed using regression method that includes randomization stratum of HbA1c ($\leq 8.5\%$, $> 8.5\%$), randomization stratum of SBP (< 130 , ≥ 130 mmHg), and baseline value in the imputation model (see sample code Part 1 or 2b in [Appendix A](#)).

Each continuous secondary endpoints (see [Section 2.1.3](#)) will be analyzed using a similar ANCOVA model including the measurements at baseline and endpoint (observed or imputed). The missing data at endpoint will be imputed by the retrieved dropouts & washout imputation method or by the control-based copy reference imputation method according to the criterion described in [Section 2.4.4.1](#). After the imputation, each of the complete datasets will be analyzed by an ANCOVA model.

The ANCOVA model with treatment groups (sotagliflozin 400 mg, sotagliflozin 200 mg, placebo), randomization stratum of HbA1c ($\leq 8.5\%$, $> 8.5\%$), randomization stratum of SBP (< 130 , ≥ 130 mmHg), and country as fixed effects, and baseline secondary endpoint value as a covariate. For the analysis of SBP in patients with baseline SBP ≥ 130 mmHg, the randomization stratum of SBP will not be included in the ANCOVA model. Results from each complete dataset will be combined using Rubin's rule to provide the adjusted mean change from baseline to Week 26 (or Week 12 for SBP) for each treatment group, as well as the between-group difference (comparing sotagliflozin 400 mg, sotagliflozin 200 mg vs placebo) and the 95% CI for the difference.

UACR will be log-transformed at patient level before analysis, and geometric means (with and without ANCOVA model adjustment), differences between treatments and 95% CIs will be back-transformed to original scale. Summary statistics of UACR in log scale will then be calculated for

each treatment group at each visit and back-transformed to provide the geometric mean and its associated percent change of UACR from baseline.

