2.4.4.4 Multiplicity issues

To control the family-wise type I error, a hierarchical testing procedure will be applied.

Once the primary variable (change from Baseline to Week 26 in HbA1c) is statistically significant at $\alpha=0.05$ (2-sided), a hierarchical testing procedure will be performed to test the following secondary efficacy variables in the following prioritized order. The testing will stop as soon as an endpoint is found not to be statistically significant at $\alpha=0.05$ (2-sided).

- Comparing sotagliflozin 200 mg versus placebo in change from Baseline to Week 26 in HbA1c
- Comparing sotagliflozin 400 mg versus placebo
 - Change from Baseline to Week 26 in FPG
 - Change from Baseline to Week 26 in body weight
 - Change from Baseline to Week 12 in SBP for patients with baseline SBP ≥ 130 mmHg
 - Change from Baseline to Week 12 in SBP for all patients
 - Proportion of patients with HbA1c $< 7.0\%$ at Week 26
- Comparing sotagliflozin 200 mg versus placebo
 - Change from Baseline to Week 26 in FPG
 - Change from Baseline to Week 26 in body weight
 - Change from Baseline to Week 12 in SBP for patients with baseline SBP ≥ 130 mmHg

Once the above secondary variables are statistically significant at $\alpha = 0.05$ (2-sided), Hochberg's step-up procedure (1) will be performed to test the remaining 4 secondary variables: order a number of m ($m=4$ here) tests by p-values (from lowest to highest) $P_{(1)} \dots, P_{(m)}$ associated with tests $H_{(1)} \dots, H_{(m)}$, find the largest k (called R) so that $P_{(k)} \leq \alpha / (m+1-k)$, conclude $H_{(1)} \dots, H_{(R)}$ statistically significant.

- Percentage change in UACR from Baseline to Week 26 for patients with UACR >30 mg/g at Baseline, comparing sotagliflozin 400 mg and 200 mg, respectively, versus placebo
- Proportion of patients with HbA1c <7.0% at Week 26, comparing sotagliflozin 200 mg versus placebo
- Change from Baseline to Week 12 in SBP for all patients comparing sotagliflozin 200 mg versus placebo.

No multiplicity adjustment will be made on other secondary efficacy variables than mentioned above.

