Appendix A Sample SAS® code for analyses of efficacy endpoints

```

* VARIABLES;
* ptid - patient identification;
* treat - treatment;
* strata1 - stratification factor 1;
* strata2 - stratification factor 2;
* value0 - value at baseline;
* value1 ... valuen - value at each post-baseline visit for a total of n visits; valuen at the endpoint visit;
* change - change from baseline;

***** Part 1: Preferred imputation method: the retrieved dropouts and washout imputation *****,;
*****
*.;

/* Part 1a, for parameters with no missing data at baseline */;

* MI in patients who prematurely discontinued IMP before the endpoint using the endpoint data from its
own group (retrieved dropouts);
proc sort data=ads;
  by treat ptid;
run;

proc mi data=ads out=disc_mi nimpute=2000 seed=97531;
  where discontinue = "Y";
  by treat;
  var value0 valuen;
  monotone regression (valuen = value0 );
run;

* MI in patients who stay on the IMP until the endpoint visit using the endpoint data from the placebo group
(wash-out MI);
proc sort data=ads;
  by ptid;
run;

proc mi data=ads out=comp_mi nimpute=2000 seed=75319;
  where discontinue="N" and (treat=1 or (treat ne 1 and valuen =. )); *1 denotes placebo group;
  class strata1 strata2;
  var strata1 strata2 value0 valuen;
  monotone regression (valuen = strata1 strata2 value0 );
run;

* Repeat dataset with the same number of replications for remaining patients who have complete data at
the endpoint visit;
data comp_trt;

```

Statistical Analysis Plan

Version: Final 3.0

Lexicon Pharmaceuticals Protocol No. EFC15166

Date of Issue: 21 November 2019

Covance Study ID: 000000155203

```
set ads (where=(discontinue="N" and treat ne 1 and valuen ne .));
_imputation_=0;
do i = 1 to 2000;
    _imputation_=_imputation_+1;
    output;
end;
run;
```

* Combine MI from the three subsets of patients;

```
data mi_1;
    set disc_mi comp_mi comp_trt;
run;
```

/*Part 1b, for parameters with missing data at baseline */

* To impute the missing data at baseline;

```
proc sort data=ads;
    by ptid;
run;
```

```
proc mi data=ads out=mi_base nimpute=2000 seed=13579;
    class strata1 strata2;
    var strata1 strata2 value0;
    monotone regression;
run;
```

* MI in patients who prematurely discontinued IMP before the endpoint using the endpoint data from its own group (retrieved dropouts);

```
proc sort data=mi_base;
    by _imputation_ treat ptid;
run;
```

```
proc mi data=mi_base out=disc_mi nimpute=1 seed=97531;

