***** Part 4: ANCOVA *****
*****
```

```
proc mixed data=mi_2;
  by _imputation_;
  class treat strata1 strata2 country;
  model change= treat strata1 strata2 country value0;
  lsmeans treat /diff cl;
  lsestimate treat "A1 Placebo" 1 0 0 /cl;
  lsestimate treat "A2 200mg drug" 0 1 0 /cl;
  lsestimate treat "A3 400mg drug" 0 0 1 /cl;
  lsestimate treat "B1 200mg drug vs Placebo" -1 1 0 /cl;
  lsestimate treat "B2 400mg drug vs Placebo" -1 0 1 /cl;
  ods output LSMEstimates=LSMEstimates;
run;
```

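### SAP Appendix D and Section 1.6 name baseline HbA1c as the ANCOVA covariate for FPG, body weight, SBP and UACR, where SAP 2.4.4.2, the protocol and the sample code use each endpoint's own baseline

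*SAP*

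**What the plan says.** SAP 2.4.4.2, which defines the analysis of the continuous secondary endpoints, specifies an ANCOVA with treatment, the two randomization strata "and country as fixed effects, and baseline secondary endpoint value as a covariate". Protocol 11.4.2.2 and the protocol synopsis give the same covariate. The sample code in SAP Appendix A agrees: its model line is "model change= treat strata1 strata2 country value0", and the variable list defines "value0 - value at baseline", meaning the baseline of whatever variable is being analysed.

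SAP Appendix D has one row for the continuous secondary endpoints: HbA1c for 200 mg versus placebo, FPG, body weight, SBP and UACR. Its primary-analysis column gives a single model for all of them, ending "and baseline HbA1c value as a covariate".

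SAP Section 1.6 adds further analyses. Their scope is stated as "The primary and continuous secondary efficacy endpoints for the overall population missing data at Week 26 (or Week 12 for SBP) visit will be imputed", and their role as "The majority of these additional assessments will serve as sensitivity analyses". The section contains one ANCOVA statement, with the strata "and country as fixed factors, and baseline HbA1c value as a covariate". The result it then names is the adjusted change in HbA1c, although the same sentence allows for Week 12 for SBP. The last paragraph of the section extends its sensitivity methods to Week 52.

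**The concern.** Two covariates are written down for the same analyses. A programmer working from Appendix D would adjust change in FPG, weight, SBP and log UACR for baseline HbA1c. A programmer working from 2.4.4.2 would adjust for the endpoint's own baseline. No text sets an order of precedence.

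Change from baseline is correlated with its own baseline by construction. Leaving that baseline out leaves removable variance in the residual and chance baseline imbalance uncorrected. In Appendix D this touches formally tested endpoints in a sequence where "The testing will stop as soon as an endpoint is found not to be statistically significant". FPG for 400 mg comes directly after HbA1c for 200 mg, so a non-significant FPG result there would block seven further ordered tests and the four Hochberg tests.

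In Section 1.6 the issue is interpretability. Those analyses are meant to show how far results depend on the missing-data method. If the covariate changes together with the imputation, a difference from the main result cannot be attributed to the imputation.

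**Working it through.** **The texts side by side**

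| Place | Covariate |
|---|---|
| Protocol synopsis and 11.4.2.2 | own baseline |
| SAP 2.4.4.2 | own baseline |
| SAP Appendix A, ANCOVA code | own baseline (value0) |
| SAP 1.6, imputation models | own baseline |
| SAP 1.6, ANCOVA paragraph | baseline HbA1c |
| SAP Appendix D, secondary row | baseline HbA1c |

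Appendix D uses the same covariate wording in the primary-endpoint row, and the Section 1.6 sentence names HbA1c as the outcome. Both look carried over from the primary model.

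**The plan's own figure**

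The only design calculation is for the primary endpoint: SD 1.2%, difference 0.5%, two-sided 0.05, 92 per group, 80% power. With n = 2(1.960 + 0.842)² × 1.2² / 0.5² = 90.4, 91 per group are needed. Power at 92 is 80.7% (80.3% by noncentral t). The figure reproduces. No power is stated for FPG, weight, SBP or UACR, so the 80% starting point below is only a reference.

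**Precision, simple form**

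Let baseline and follow-up have equal SD s and correlation ρ (assumed), and let baseline HbA1c be unrelated to the change.

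- Residual variance of change without the own baseline: 2s²(1 − ρ)
- Residual variance with it: s²(1 − ρ²)
- Ratio: 2/(1 + ρ)
- Power of a test that has 80% under the own-baseline model: Φ(2.802/√ratio − 1.960)

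| ρ | Ratio | SE increase | Power, from 80% |
|---|---|---|---|
| 0.3 | 1.538 | 24.0% | 61.7% |
| 0.5 | 1.333 | 15.5% | 67.9% |
| 0.7 | 1.176 | 8.5% | 73.3% |
| 0.9 | 1.053 | 2.6% | 78.0% |
| 0.98 | 1.010 | 0.5% | 79.6% |

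**Precision with the strata in both models**

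The strata recover part of the loss, so the comparison was repeated by large-sample regression (400,000 simulated patients) with both dichotomised strata in each model, contrasting baseline HbA1c with the own baseline. All correlations are assumed:

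- Screening with baseline HbA1c: 0.9
- Baseline HbA1c with baseline FPG: 0.3 or 0.6; with weight 0.05; with log UACR 0.1; with SBP 0
- Screening with baseline SBP: 0.6

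Country was left out. Baseline HbA1c was given no predictive value for follow-up beyond the own baseline.

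| Endpoint | ρ | SE increase | Power, from 80% |
|---|---|---|---|
| FPG (HbA1c correlation 0.3) | 0.3 / 0.5 / 0.7 | 22.1 / 14.2 / 7.7% | 63.1 / 68.9 / 74.0% |
| FPG (HbA1c correlation 0.6) | 0.3 / 0.5 / 0.7 | 15.7 / 10.1 / 5.5% | 67.7 / 72.1 / 75.7% |
| SBP, all patients | 0.3 / 0.5 / 0.7 | 19.5 / 12.4 / 6.8% | 64.9 / 70.3 / 74.6% |
| Log UACR | 0.7 / 0.8 / 0.9 | 8.2 / 5.3 / 2.5% | 73.5 / 75.9 / 78.0% |
| Body weight | 0.95 / 0.98 | 1.3 / 0.5% | 79.0 / 79.6% |

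The HbA1c-adjusted model was the less precise in every case tried. The subset with baseline SBP of at least 130 mmHg was not modelled separately.

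**The case against.** The strongest reply is that the intended model is clear. The protocol, the SAP section that defines these analyses, and the sample code all use the own baseline. Appendix D is a summary table; its secondary cell also omits the 2.4.4.2 rule that drops the SBP stratum in the subset with elevated baseline SBP. In Section 1.6, a reader must already replace HbA1c by the endpoint for the sentence to make sense for SBP at Week 12, and the covariate could follow by the same reading. This stands as evidence of intent. It does not remove the conflict, because no precedence is stated and Section 1.6 offers no other ANCOVA covariate.

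Several stronger readings are tempting, and the documents do not support them.

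- *Every continuous secondary analysis has the wrong model.* HbA1c for 200 mg versus placebo is in the same row, and baseline HbA1c is its own baseline.
- *Section 1.6 endangers the hierarchy.* Its analyses are additional, mostly sensitivity, and outside the testing sequence. It is scoped to the overall population, so its reach to the UACR and SBP subsets is not explicit either.
- *The Week 52 comparisons are misspecified.* Section 1.6 repeats the main analyses at Week 52 as set out in 2.4.4.1 and 2.4.4.2, hence with the own baseline. Only the Week 52 sensitivity analyses inherit the problem.
- *The covariate was left open until Week 26 results were known.* Section 1.6 does report that the first-step analysis preceded this SAP version. But the SAP dates protocol amendment 1 to December 2017, less than 26 weeks after the first enrolment on 12 September 2017, and that amended protocol specifies the own baseline.

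**Conclusion.** The contradiction is real and should be corrected. It is a defect of specification and precision. A reader might infer bias or an inflated type I error, but both models give unbiased treatment effects under randomization, and the error rate holds provided one model is fixed independently of the results.

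The size depends on correlations the documents do not give. Under the assumed ranges, the loss could matter for FPG and SBP, is modest for log UACR and is negligible for body weight. A reader might apply the simple ratio at ρ of 0.5 to 0.8 and conclude that about 10% to 25% of the sample is lost for all these endpoints (1 − 1/1.111 and 1 − 1/1.333). That range is not supported as a common figure: it ignores the strata and does not fit body weight.

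The Appendix D conflict is the one that bears on formal testing. The Section 1.6 conflict bears on how cleanly the sensitivity analyses, including their Week 52 extension, can be read against the main analysis.

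**What to change.** Bring both places into line with SAP 2.4.4.2:

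- In the secondary row of Appendix D and in the Section 1.6 ANCOVA paragraph, replace baseline HbA1c as covariate with the baseline value of the corresponding endpoint, on the log scale for UACR. This wording remains correct for HbA1c 200 mg versus placebo.
- In the same Section 1.6 paragraph, change the reported result from the adjusted mean change in HbA1c to the adjusted mean change in the endpoint.

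The cost is a few words in two places. No design figure changes, and neither the sample code nor the protocol needs editing.
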